4. OVERVIEW OF STUDY DESIGN AND METHODOLOGY

4.1. Study Design

This is an open-label, single-center Phase I dose escalation trial designed to determine the cumulative MTD in a dose fractionation regimen in which ¹⁷⁷Lu-PSMA-617 will be given in 2 doses, 2 weeks apart. The dose escalation will start at 100 mCi (3.7 GBq) x 2 doses and escalate in increments of 50 mCi (1.85 GBq) for each dose to a maximum of 300 mCi (11.1 GBq) x 2 doses.

Patients must have documented progressive metastatic CRPC disease based on Prostate Cancer Working Group 3 (PCWG3) criteria in order to be eligible for enrollment. Upon meeting the inclusion and exclusion criteria and signing the informed consent and HIPPA form, subjects will undergo the screening. As part of the screening, subjects will get a single dose of ⁶⁸Ga-PSMA-HBED-CC and will have a PET/CT. Nuclear Medicine physician(s) will review the PET/CT scans to document PSMA expression at tumor site(s).

¹⁷⁷Lu-PSMA-617 dose fractionation regimen will be performed in patients with documented progressive metastatic CRPC. The ¹⁷⁷Lu dose (50 mCi – 300 mCi or 1.85 – 11.1 GBq) will be escalated in up to 6 different dose levels (3+3 at each dose level). Initially 3 subjects will be enrolled in Cohort 1 (100 mCi or 3.7 GBq x2 doses 2 weeks apart) and if any grade ≥ 3 toxicity is reported, then the next 3 subjects will be enrolled

in Cohort -1 (50 mCi or 1.85 GBq x2 doses 2 weeks apart) before proceeding to higher dose cohorts. Subjects will have Lutetium-177 Planar/SPECT Imaging on Day 8 (± 1 day) after the first dose of ^{177}Lu -PSMA-617. Optimal images will be performed on selected consenting subjects between initial treatment on D1 and D4 and prior to treatment #2 on D15. The enrollment ceiling of the dose escalation portion of the study is up to 46 study participants (six groups, with 3+3 subjects in each group). Each patient would receive 2 doses of the investigational agent, 2 weeks apart. The total dose received in 2 treatments will be **100 – 600 mCi (3.7 – 22.2 GBq)**.

Upon completion of investigational treatment with 2 doses of ^{177}Lu -PSMA-617, subjects will undergo ^{68}Ga -PSMA-HBED-CC injection and same day PET/CT at the end of study visit to document treatment response. Subsequently survival data and additional treatment(s) information will be captured from their routine Standard of care (SOC) visits.

Table 7: Treatment Plan with ^{177}Lu -PSMA-617

Cohort	Treatment Dose mCi (GBq)		Total mCi (Dose GBq)	Subjects (n)
	Day 1	Day 15			
-1	50 (1.85)	50 (1.85)	100 (3.7)	1-6
1	100 (3.7)	100 (3.7)	200 (7.4)	1-6
2	150 (5.55)	150 (5.55)	300 (11.1)	1-6
3	200 (7.4)	200 (7.4)	400 (14.8)	3-6
4	250 (9.25)	250 (9.25)	500 (18.5)	3-6
5	300 (11.1)	300 (11.1)	600 (22.2)	3-6

4.2 Rationale for Dose-Escalation Strategy:

This study will use a modified phase I 3+3 dose-escalation study design, with the planned initial and subsequent cohorts described in Table 7. This study design is well-described and accepted by the clinical and scientific community, so we will not provide complete details here. Briefly, this design is constructed to reduce the chance of escalating the dose when the probability of DLT is high, and increase the chance of escalating the dose when the probability of DLT is low. Given the fact that some pre-existing clinical efficacy and toxicity data exists with the study drug, we will allow up to 6 subjects to be treated at a given dose-level even in the absence of DLT. The MTD is defined as the highest dose level with an observed incidence of DLT in no more than one out of six patients treated at a particular dose level. The dose escalation scheme provides the following probabilities of escalation based on the true chances of DLT at a specific dose level. One can see that the probability of escalation is high if the toxicity risks are low:

True Probability of Toxicity:	.05	.10	.20	.30	.40	.50	.60
Probability of Escalation:	.97	.91	.71	.49	.31	.17	.08

As there is a reasonably large pool of short- and long-term experience with PSMA-directed 177Lu, we will transition to a phase II cohort will be enrolled at the MTD/RP2D to gain additional safety data as well as preliminary efficacy data. We will enroll up to 27 subjects in the Phase II trial utilizing a Simon two-stage design (including the 3-6 patients used for establishing the MTD). For the phase II portion, we will define evaluable patients as those who met eligibility requirements, have initiated therapy, and were not removed from the study for non-compliance or withdrawal. Sample size recommendations for the two-stage design are determined according to Simons two-stage minimax design. The first stage will accrue a total of 16 patients (including those who were treated at the MTD in the phase I portion), if 6 or fewer of the first 16 evaluable patients do not experience a 30% decline in PSA, the study will be terminated and declared to have a negative result. If 7 or more patients out of the first 16 evaluable patients experience a 30% decline in PSA, 9 more patients will be accrued in Stage 2 (total sample size of 27). The new regimen will be declared to have activity and be worthy of further testing if 13 or more patients experience a 30% PSA decline among the 27 patients who are part of the phase II trial.

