6.2.4. Dose levels for ^{177}Lu -PSMA-617

Subject(s) enrollment will be done as 3+3 study design at each dose level. Initially at least 3 subject(s) will be enrolled in Cohort 1 (100 mCi or 3.7 GBq x2 doses 2 weeks apart) with dose escalation (or de-escalation as described above in Section 4 / Table 7).. The enrollment ceiling of the dose escalation portion of the study is up to 46 study participants (six groups, with 3+3 at each dose level). Additional 10 subjects will be enrolled at the MTD dose level to further assess safety and tolerability and to obtain a preliminary assessment of efficacy. Each patient would receive 2 doses of the investigational agent, 2 weeks apart. The total dose received in 2 treatments in phase 1 will be 100 – 600 mCi or 3.7 – 22.2 GBq. The total dose for phase 2 is 600 mCi (22.2 GBq).

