6.2.9. Imaging Plan

A. ^{68}Ga -PSMA-HBED-CC PET/CT Scan

Patient preparation should be according to the policies and procedures of the local imaging site (CIBC). The patient does not need to be fasting for either the infusion or

the scans. The use of intravenous or oral contrast will not be permitted. Specifications for acquiring the ⁶⁸Ga-PSMA-HBED-CC PET/CT scans will be provided in study specific documentation by the study chair or the co-investigators from the Division of Nuclear Medicine. PET/CT should be obtained during the Screening Visit as well as at the end of study visit. The images are acquired between 1 and 3 hours after the ⁶⁸Ga-PSMA-HBED-CC infusion. Image acquisition will be from vertex of skull to mid thighs.

B. ¹⁷⁷Lu-PSMA-617 Planar/SPECT imaging

Patient preparation should be according to the policies and procedures of the local imaging site (CIBC). The patient does not need to be fasting for either the infusion or the scans. The use of intravenous or oral contrast will not be permitted. Specifications for acquiring the ¹⁷⁷Lu-PSMA-617 planar/SPECT images will be provided in study specific documentation by the study chair or the co-investigators from the Division of Nuclear Medicine. Planar/SPECT images should be obtained during the Imaging Visit (Day 8 ±1) on all subjects after the ¹⁷⁷Lu-PSMA-617 infusion. Image acquisition will be from vertex of skull to mid thighs. Optional images will be performed on selected consenting subjects between initial Treatment Visit (between D1 - D4) and prior to Treatment Visit 2 (Day 15 ±1).

Managing toxicity

NCI CTCAE version 4.0 is used to grade all adverse events.

- Grade ≥ 2 thrombocytopenia or neutropenia within 24 hours of the second dose of ¹⁷⁷Lu-PSMA-617 (Treatment Visit 2) requires a subject's treatment to be held until the toxicity has resolved to least grade 1. If the toxicity has not resolved after 2 weeks of monitoring, the subject's ¹⁷⁷Lu-PSMA-617 treatment will be permanently discontinued and will be termed dose-limiting toxicity.

Dose-limiting toxicity (DLT) is defined as:

- Grade 4 hematologic toxicity that is deemed at least possibly related to ¹⁷⁷Lu-PSMA-617 will be termed dose-limiting toxicity.
- Any grade > 2 non-hematologic toxicity deemed to be at least possibly related to ¹⁷⁷Lu-PSMA-617 will require a subject's ¹⁷⁷Lu-PSMA-617 treatment to be permanently discontinued and will be termed dose-limiting toxicity.

Maximum Tolerated Dose (MTD) is defined as:

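### The Cohort 1 trigger for Cohort -1 in Section 4.1 conflicts with the protocol's DLT definition, its 3+3 rule and its printed escalation probabilities

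*Combined protocol and SAP*

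**What the plan says.** Section 4.1 treats 3 subjects at Cohort 1 and continues: "if any grade ≥ 3 toxicity is reported, then the next 3 subjects will be enrolled" in Cohort -1, "before proceeding to higher dose cohorts". The sentence does not ask whether the event is related to study drug, does not separate hematologic from other events, and does not count DLTs.

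The other sections that bear on the same decision are these.

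- Section 6.2.4: "Subject(s) enrollment will be done as 3+3 study design at each dose level". Section 4.1 itself also describes the levels as 3+3. For de-escalation, Section 6.2.4 points back to Section 4 and Table 7.
- Managing toxicity (printed under Section 6.2.9, listed as 6.2.10 in the contents) gives three routes to a DLT. The first is "Grade 4 hematologic toxicity that is deemed at least possibly related to" the study drug. The second is "Any grade > 2 non-hematologic toxicity deemed to be at least possibly related to" it. The third is grade 2 or higher thrombocytopenia or neutropenia at the second dose: "If the toxicity has not resolved after 2 weeks of monitoring", treatment stops and the event is termed a DLT.
- Sections 4.2 and 12.1: "The dose escalation scheme provides the following probabilities of escalation based on the true chances of DLT at a specific dose level". Seven probabilities follow. Both sections define the MTD as the highest level with no more than one DLT in six patients.
- Section 4.2 calls the design a modified 3+3, explains the modification as allowing up to 6 subjects at a level without any DLT, and declines to give the full rule.

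**The concern.** The event that moves subjects at Cohort 1 is not the event that defines the MTD, and the action taken is not the 3+3 action. There are three mismatches.

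1. A grade 3 hematologic event triggers Cohort -1, although it is not a DLT unless it is a thrombocytopenia or neutropenia still unresolved after the two-week hold at dose 2.
2. An unrelated grade 3 or higher event triggers Cohort -1, although it cannot meet the grade-based DLT criteria, which require at least possible relation.
3. After a single DLT in 3, the 3+3 adds 3 subjects at the same level. Section 4.1 sends the next 3 to Cohort -1.

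Related non-hematologic events are not part of the event mismatch: grade 3 or higher and grade above 2 are the same threshold.

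Two sites following different sections could assign the next three subjects to different doses after the same event. The MTD is a phase I primary objective, and the printed operating characteristics would not describe the first dose level. The sentence also states no DLT-count condition for moving up after Cohort -1, so the reader must take that from elsewhere.

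**Working it through.** **Inputs.** The printed table and the one-in-six MTD rule are from Sections 4.2 and 12.1. The DLT definition is from Managing toxicity. The trigger is from Section 4.1. The 12% rate of grade above 2 hematologic events is from the German multicenter retrospective series in Section 2.3.1. The plan gives no rate q of any grade 3 or higher event for this trial, so every q below is an assumption.

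**Step 1: reproduce the printed table.** For a true DLT rate p, escalating on 0/3, or on 1/3 followed by 0/3, has probability

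P(escalate) = (1-p)^3 + 3p(1-p)^2 × (1-p)^3.

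At p = 0.05: 0.8574 + 0.1354 × 0.8574 = 0.973. At p = 0.10: 0.729 + 0.243 × 0.729 = 0.906.

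| p | 0.05 | 0.10 | 0.20 | 0.30 | 0.40 | 0.50 | 0.60 |
|---|---|---|---|---|---|---|---|
| Printed | .97 | .91 | .71 | .49 | .31 | .17 | .08 |
| 3+3 formula | .973 | .906 | .709 | .494 | .309 | .172 | .082 |
| No event in 3, (1-p)^3 | .857 | .729 | .512 | .343 | .216 | .125 | .064 |

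All seven values match. Three alternatives do not: six patients treated and at most one DLT allowed gives .886 at p = 0.10; tolerating two in six gives .965 (stopping at 2/3) or .985 (expanding at 2/3). So the rule behind the table counts DLTs and expands the same level after one.

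**Step 2: apply the Section 4.1 sentence.** The next 3 go to Cohort -1 if at least one of 3 has a trigger event: P(detour) = 1 - (1-q)^3.

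- q = 5%: 1 - 0.95^3 = 14%; no detour 86%.
- q = 10%: 1 - 0.90^3 = 27%; no detour 73%.
- q = 12%: 1 - 0.88^3 = 32%; no detour 68%.

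**Step 3: separate the two sources of difference.**

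*Action.* Suppose trigger events were exactly DLTs (q = p). The no-detour chance would still be 86% against 97%, and 73% against 91%. The gap is the lost expansion route, 3p(1-p)^5: 0.1354 × 0.8574 = 0.116 at 5%, and 0.243 × 0.729 = 0.177 at 10%. Exactly one DLT in 3, where the two rules give different instructions, has probability 3p(1-p)^2 = 14%, 24%, 38% and 44% at p = 5%, 10%, 20% and 30%.

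*Event.* Let d be the DLT rate and n the rate of patients with a grade 3 or higher event but no DLT. A detour with no DLT in the cohort has probability (1-d)^3 - (1-d-n)^3. With d = 5% (assumption):

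- n = 5%: 0.857 - 0.90^3 = 0.857 - 0.729 = 13%.
- n = 12%: 0.857 - 0.83^3 = 0.857 - 0.572 = 29%.
- n = 30%: 0.857 - 0.65^3 = 0.857 - 0.275 = 58%.

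In each of these the 3+3 sees 0/3 DLTs and escalates.

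**The case against.** The strongest reply is that this is a cautious extra step at one level. It uses a cohort already in Table 7, errs toward a lower dose, and leaves the DLT and MTD definitions untouched. That is fair as to direction, and a sponsor may want a stricter first-level rule. It does not remove the conflict, because the plan does not present the rule as an exception: Section 4.1 describes 3+3 at each level, and the modification explained in Section 4.2 is a different one.

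A reader might infer that two or three DLTs at Cohort 1 need not block escalation, since Section 4.1 goes on to higher cohorts. The documents do not support that. The sentence is silent on DLT counts and does not authorize escalation. Counted from Cohort -1, the higher cohorts include Cohort 1. The rule behind the table gives no chance of escalation after 2/3 or 3/3, and the one-in-six MTD rule would also stop it. Section 12.6 adds safety analyses before each escalation, and Section 14 adds DSMB notification. Section 12.5.1 does tolerate two DLTs in a cohort, but that is a separate inconsistency among the MTD definitions; three DLTs exceed both limits.

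Nor does the text close Cohort 1 after a detour: Table 7 allows up to 6 subjects there.

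Two further cautions stand. The 12% comes from a retrospective chart review in which retreatment was allowed. And the 32% should not be set against the table's 3% to 9% chance of not escalating: a detour is not a failure to escalate. The comparable 3+3 figure is at least one DLT in 3, which is 14% at p = 5% and 27% at p = 10%.

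Finally, Section 6.2.4 fixes the phase II total at 600 mCi, the Cohort 5 total. This suggests, but does not state, that escalation is finished.

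**Conclusion.** The conflict is real and no section resolves it. It covers grade 3 hematologic events that are not DLTs, unrelated events, and the action after a single DLT. The missing DLT-count condition after Cohort -1 is a gap in the sentence, limited by the MTD rule in Sections 4.2 and 12.1; it is not permission to escalate through DLTs.

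The table match is exact. The 86% and 73% assume trigger rates of 5% and 10% and describe moving up without a detour, not the chance of ever reaching a higher dose. The 32% assumes that the background 12% applies here. Which Cohort 1 rule is clinically right is not for this review. The point merits correction because dose assignment and a primary endpoint depend on it. If escalation is complete, what remains is to make the Cohort 1 result interpretable.

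**What to change.** Reconcile Sections 4.1, 4.2, 6.2.4, Managing toxicity and 12.1 so that one written rule governs Cohort 1: the event that counts, whether attribution is required, how many events, and the next step, including what follows Cohort -1. The sponsor makes the clinical choice.

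If the Cohort 1 rule stays different from the 3+3 behind the table, add to Sections 4.2 and 12.1 that the printed escalation probabilities do not apply to Cohort 1. If escalation is already complete, state which rule was applied there.

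The cost is a short text amendment, with no added patients or procedures.

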12.2. Phase II

We will enroll up to 27 subjects into the Phase II portion (including the 3-6 used for establishing the MTD). We will define evaluable patients as patients who met eligibility requirements, have initiated therapy, and were not removed from the study for non-compliance or patient withdrawal.

Sample size recommendations for the two-stage design are determined according to Simon's two-stage minimax design. We project a 30% PSA decline proportion of 35%, below which the regimen will be unacceptable and a 30% PSA decline proportion of 60%, above which the regimen will be considered worthy of further exploration. The null hypothesis that the 30% PSA decline proportion is less than or equal to 35% will be tested against the alternative hypothesis that the 30% PSA decline proportion is greater than or equal to 60%.

The sample size computations were performed assuming a 0.10 one-sided level of significance and 90% power assuming a historical control value for PSA decline of 35% and the alternative hypothesis of 60%. If 6 or fewer of the first 16 evaluable patients do not experience a 30% decline in PSA (stage 1), the study will be terminated and declared to have a negative result. If 7 or more patients out of the first 16 evaluable patients experience a 30% decline in PSA, ongoing accrual will proceed to the target sample size of 27 patients (stage 2). The new regimen will be declared active in this patient population and worthy of further testing if 13 or more patients experience a 30% PSA decline among the 27 patients entered. This two-stage design yields a 0.90 probability of a positive result if the true 30% PSA decline proportion is 60%. It yields a 0.90 probability of a negative result if the true 30% PSA decline proportion is 35%. An exact 95% binomial confidence interval will be constructed for the proportion of patients with PSA decline.

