12.3. Sample Size/Accrual Rate

The planned sample size for this dose escalation Phase I study is between 6-36 and between 16-27 for phase II. The accrual rate is anticipated to be 1-2 patients/month on average (with expected pauses between dose-escalation cohorts and between stage 1 and stage 2 of the phase II trial).

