12.4. Stratification Factors

This is not a randomized trial and there are no planned stratification factors. Descriptive statistics will be utilized. Stopping rules for futility are in place as per Section 4.2.

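### Accrual figures do not add up: nine stage 2 patients cannot take 16 to 27, six groups of 3+3 are 36 rather than 46, and ten additional patients cannot complete phase II

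*Combined protocol and SAP*

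**What the plan says.** **Phase II total.** Section 4.2 describes a Simon minimax design whose first stage has 16 patients, including those treated at the MTD in phase I. If seven or more of the 16 have a 30% PSA decline, "9 more patients will be accrued in Stage 2 (total sample size of 27"). Success is 13 or more responders among the 27. Section 12.2 gives the same stage 1 size and cut-offs but no stage 2 increment: "ongoing accrual will proceed to the target sample size of 27 patients (stage 2"). Its design inputs are a null proportion of 35% and an alternative of 60%, "assuming a 0.10 one-sided level of significance and 90% power".

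**Escalation ceiling.** Section 4.1 allows "up to 46 study participants (six groups, with 3+3 subjects in each group"), and section 6.2.4 repeats "up to 46 study participants (six groups, with 3+3 at each dose level"). The synopsis gives a phase I maximum of 36. Table 7 lists six cohorts, none larger than six. Section 12.3 says the sample size "is between 6-36 and between 16-27 for phase II".

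**Patients added at the MTD.** Section 6.2.4 adds ten. The synopsis adds 10 to 21 under the two-stage design, up to 27 with the phase I patients counted. Sections 4.2 and 12.2 put the number carried over from phase I at three to six.

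**The concern.** Each of these figures tells sites how many men to enrol, and each disagrees with another figure in the current text.

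The stage 2 increment matters most because it governs accrual for the phase II efficacy test. It contradicts its own parenthesis, and it sits in the section that section 12.4 cites as the home of the stopping rule: "Stopping rules for futility are in place as per Section 4.2". A team that enrolled nine would stop two short of the number to which the success cut-off belongs, and would lose power.

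The other two figures give conflicting limits: a reader of section 4.1 or 6.2.4 could accept ten more escalation patients than section 12.3 plans, and a reader of section 6.2.4 alone would see no provision for stage 2.

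**Working it through.** **Inputs.** From section 12.2: p0 = 0.35, p1 = 0.60, one-sided alpha 0.10, power 0.90, minimax design. From sections 4.2 and 12.2: n1 = 16, continue at 7 or more responders, succeed at 13 or more of 27. The futility sentence in both sections is worded in terms of patients who do not have a decline. The calculation uses the evident intention, stopping if six or fewer of 16 respond; that wording is a separate problem.

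**Formula.** With X ~ Bin(16, p) in stage 1 and Y ~ Bin(n − 16, p) in stage 2,

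P(success | p) = Σ (x = 7 to 16) P(X = x) · P(Y ≥ 13 − x).

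Alpha is this at p = 0.35 and power is this at p = 0.60.

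**The plan's own design first, then the nine-patient reading.**

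| Stage 1 + stage 2 | Success at | Alpha | Power |
|---|---|---|---|
| 16 + 11 = 27 | ≥ 13 | 0.0979 | 0.9001 |
| 16 + 9 = 25 | ≥ 13 | 0.0579 | 0.8361 |
| 16 + 9 = 25 | ≥ 12 | 0.1123 | 0.8997 |

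The first row reproduces section 12.2. The probability of stopping after stage 1 is P(X ≤ 6) = 0.688 at p0 and 0.058 at p1. The expected sample size at p0 is 16 + 11 × (1 − 0.688) = 19.4. The last row shows that lowering the cut-off does not rescue a total of 25: alpha exceeds 0.10 and power is just under 0.90.

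**Is 27 the minimax total?** A search over stage 1 sizes and cut-offs found no two-stage design with a total of 26 or fewer that has alpha ≤ 0.10 and power ≥ 0.90. The first feasible total is 27, and among the feasible designs there, 16 then 27 with these cut-offs has the smallest expected size at p0. So 27 is right, and the increment is 27 − 16 = 11. The 16 already includes the carried-over phase I patients, so they cannot supply the missing two.

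**Escalation ceiling.** Six groups × (3 + 3) = 36, and 46 − 36 = 10 too many. The design is a modified 3+3, but the modification does not raise the cap of six per level: "we will allow up to 6 subjects to be treated at a given dose-level even in the absence of DLT".

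**Additional patients at the MTD.**

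| Carried over | Total after 10 more | More needed for 16 | More needed for 27 |
|---|---|---|---|
| 3 | 13 | 16 − 3 = 13 | 27 − 3 = 24 |
| 6 | 16 | 16 − 6 = 10 | 27 − 6 = 21 |

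Ten more completes stage 1 only if six are carried over, and it never reaches 27. The synopsis range of 10 to 21 is the six-carried-over row.

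**Overall ceiling of 63 (synopsis).** 36 + 27 = 63, which counts the carried-over patients twice. Distinct patients number at most 36 + 21 = 57 with six carried over. With three carried over, phase I is at most 5 × 6 + 3 = 33, and 33 + 24 is again 57. As an upper limit, 63 is not breached, so this is a point to clarify and not an error.

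**The case against.** The strongest reply is that the nine is a slip that the text corrects for itself. Section 4.2 states 27 three times, once in the same clause as the nine. Section 12.2 has only 27, and the synopsis and section 12.3 agree. The power of 0.836 requires stopping at 25 while keeping a cut-off that both sections tie to 27 patients, so it is not a property of the plan. The nine also belongs to the continuation clause and leaves the stage 1 stopping decision untouched. All of this stands, and it limits the consequence. It does not make 16 + 9 equal 27.

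On the 46, registration is central, each cohort is capped at six, and the DSMB is notified before each escalation, so the figure would not by itself put extra patients into a cohort. That is fair as to practical effect. One might also read 46 as 36 plus a ten-patient expansion. However, both sections call it the ceiling of the escalation portion and explain it as six groups of 3+3, and section 6.2.4 adds the ten separately in its next sentence. A replacement allowance is another possible source, but section 12.7.2 mentions replacement without giving any number.

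On the ten, it is the lower end of the synopsis range and completes stage 1 when six are carried over, so it may fairly be called incomplete. The sentence still gives a single number without reference to stage 2, and that number cannot deliver the planned 27.

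**Conclusion.** The concern holds on all three counts and should be fixed. The stage 2 increment is short by two (9 against 11), the escalation ceiling is too high by ten (46 against 36), and the ten additional patients give 13 to 16 in total against a planned 27.

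The design in section 12.2 is sound: alpha 0.098, power 0.900, and the smallest total that meets the stated limits. The planned analysis is therefore intact if 27 is followed. The fall in power to 0.836 (alpha 0.058) arises only if nine are enrolled and the 13-responder rule is kept. These figures assume the intended stage 1 rule (stop at six or fewer responders of 16) and the stated 35% and 60%. The three count conflicts depend on none of these assumptions.

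**What to change.** - **Section 4.2:** change the stage 2 increment from 9 to 11.
- **Sections 4.1 and 6.2.4:** change the escalation ceiling from 46 to 36.
- **Section 6.2.4:** replace the ten additional patients with the number needed to reach 16 for stage 1 and 27 for stage 2, consistent with the synopsis.
- **Clarify, one sentence each:** state the basis of the overall ceiling of 63 or restate it, since distinct patients number at most 57 before any replacements; and align the synopsis range of 10 to 21 with the three to six carried over, which allows up to 24.

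These are text corrections. The total of 27, the cut-offs and the error rates in section 12.2 do not change, and no new calculation is needed.
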